During the treatment period, visits will occur approximately every 4 weeks for assessments of efficacy and safety as per the assessment schedule (see Table 8-1). Safety assessments will include physical examinations, ECGs, vital signs, standard clinical laboratory evaluations (hematology, blood chemistry, and urinalysis), and adverse event and serious adverse event monitoring. Right heart catheterization to measure PVR for the primary objective and primary efficacy endpoint is performed at the end of the treatment period on Day 169 (Week 25). Other measures of efficacy include echocardiography (Week 5, Week 13, and Week 25) and the 6MWT (Week 5, Week 13, and Week 25). PAH-SYMPACT and emPHasis-10 will be collected for 7 day intervals with the seventh day of collection occurring within the allotted visit window for the following visits: Day 1, Week 5, Week 9, Week 13, Week 17, Week 21, and Week 25.

Following the end of the treatment period, participants will have one follow-up visit approximately 30 days after end of treatment (Week 29), which will serve as the End of Study (EOS) visit. All visits from Week 5 to Week 25 have a plus 5 day visit window and Week 29 has a plus or minus 5 day visit window. If treatment is ended early for any reason, the end of treatment visit procedures should occur as soon as possible thereafter.

An unblinded interim analysis (IA) is planned for when approximately 20 participants complete the 24-week treatment period, and may include analyses to assess sample size, efficacy, PK, PD, or safety. The analysis may be used for internal decision making of the further development of LTP001 in PAH patients. Further analyses will be prepared for review by the DMC per the DMC charter.

Pending the safety and efficacy profile of LTP001 that is observed in the current study (absence of study treatment discontinuation criteria or study stopping rules or an emerging safety concern in the review of the data), participation in the open label extension study may be offered to participants once the extension study is approved by the competent authorities and review boards.

Transition from the current study in an open label extension (OLE) study will be defined in the separate protocol. For participants enrolling into the OLE study, the EOS visit will be skipped in order to continue treatment in the OLE protocol. Replacement of such procedures done at the EOS will be defined in the OLE study protocol.

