- 8. History of malignancy of any organ system (other than localized basal cell carcinoma of the skin or *in-situ* cervical cancer), treated or untreated, within the past 5 years, regardless of whether there is evidence of local recurrence or metastases.
- 9. Women of child-bearing potential, defined as all women physiologically capable of becoming pregnant, **unless** they are using highly effective methods of contraception while taking study treatment and until End of Study visit (30 days post-last treatment). Highly effective contraception methods include:
  - · Total abstinence (when this is in line with the preferred and usual lifestyle of the participant). Periodic abstinence (e.g. calendar, ovulation, symptothermal, post-ovulation methods) and withdrawal are not acceptable methods of contraception.
  - · Female sterilization (have had surgical bilateral oophorectomy with or without hysterectomy), total hysterectomy, or bilateral tubal ligation at least six weeks before taking study treatment. In case of oophorectomy alone, only when the reproductive status of the woman has been confirmed by follow up hormone level assessment.
  - · Male sterilization (at least 6 months prior to screening). For female participants on the study, the vasectomized male partner should be the sole partner for that participant
  - · Use of oral, (estrogen and progesterone), injected, or implanted hormonal methods of contraception or placement of an intrauterine device (IUD) or intrauterine system (IUS), or other forms of hormonal contraception that have comparable efficacy (failure rate < 1%), for example hormone vaginal ring or transdermal hormone contraception.

In case of use of oral contraception women should have been stable on the same pill for a minimum of 3 months before taking study treatment.

Women are considered post-menopausal if they have had 12 months of natural (spontaneous) amenorrhea with an appropriate clinical profile (e.g. age appropriate history of vasomotor symptoms). Women are considered not of child bearing potential if they are post-menopausal or have had surgical bilateral oophorectomy (with or without

Page 38 of 94

hysterectomy) or total hysterectomy at least six weeks ago. In the case of oophorectomy alone, only when the reproductive status of the woman has been confirmed by follow up hormone level assessment is she considered not of child bearing potential.

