## 8 Visit schedule and assessments

The Assessment Schedule (Table 8-1) lists all of the assessments when they are performed. All data obtained from these assessments must be supported in the participant's source documentation.

Participants should be seen for all visits/assessments as outlined in the assessment schedule (Table 8-1) or as close to the designated day/time as possible. Missed or rescheduled visits should not lead to automatic discontinuation.

The following visits may be conducted at an off-site location as allowed by local laws and regulations: Visit 120 (Week 9), Visit 140 (Week 17), Visit 150 (Week 21), and Visit 199 (Week 29).

For all visits, assessments may occur throughout the visit window over multiple days, as needed, except where defined. For Day 1 and Week 25 visits with timed PK draws, only PK samples need to be taken post-dose.

On clinic visit days, the participant should take LTP001 during the clinic visit prior to post-dose PK samples (when applicable), when instructed by the study staff. RHC assessments and 6 minute walk test assessments should be executed at approximately the same time after drug administration each time (+/- 1 hour).

Participants who discontinue from study treatment are to return for the end of treatment visit as soon as possible, and attend the follow-up visits as indicated in the Assessment Schedule.

Participants who discontinue from study or withdraw their consent/oppose the use of their data/biological samples should be scheduled for a final evaluation visit if they agree, as soon as possible, at which time all of the assessments listed for the final visit will be performed. At this final visit, all dispensed investigational product should be reconciled, and the adverse event and concomitant medications not previously reported must be recorded on the eCRF.

[figure not shown]
The "X" in the table denotes the assessments to be recorded in the clinical database or received electronically from a vendor. The "S" in the table denotes the assessments that are only in the participant's source documentation and do not need to be recorded in the clinical database.

Table 8-1 Assessment Schedule

Period	Screening						Т	reatr	nent								EOS
Visit Name	Screening 2				Trea	tment								EC	т		EOS 
Visit Numbers 	1		100					12 0	13 0	14 0	15 0			16	0		1999
Days	-56 to -1		1					57 +5	85 +5	11 3 +5	14 1 +5			16 +			199 ±5
Weeks	-8 to -1			1			5	9	13	17	21			2	5		29

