Weeks	-8 to -1		1 5 9 13 17 21 25												29		
Time (post- dose)	-	Predos e							-	-	-	-	0mi n	15mi n	45mi n	120mi n	-
Echocardiogram	Х	•					Χ		Χ			Χ					
6-Minute Walk Test	X 	9															
Concomitant Medications/ Adverse Events			As required														
Serious Adverse Events		X															
Study completion information		X															

<sup>X Assessment to be recorded in the clinical database or received electronically from a vendor

<sup>S Assessment to be recorded in the source documentation only

<sup>1 Visit structure given for internal programming purpose only

<sup>2 All assessments during screening must be done at the clinic site.

<sup>3 Short physical exam may be employed beginning at Week 5, unless complete physical exam is indicated.

<sup>4 Only to be conducted if historical lung function testing within 24 months of screening is not available.

 

 

PROs to be completed by participants for 7 consecutive day intervals beginning 6 days prior to Day 1 and 7 day intervals around each visit from Weeks 5 to 25. The 7th day of collection for each visit should occur during the Visit Window for Weeks 5 to Week 25.

<sup>9 On clinic visit days, PROs are to be the first assessments performed.

<sup>11 Dosing is daily from Day 1 to Week 25 including all visit and non-visit days.

<sup>12 Collect unused study medication, perform drug accountability (pill count) and document compliance with protocol instructions.

Period	Screening						Т	reatı	nent								EOS
Visit Name	Screening 2		Treatment					EOT									EOS 
Visit Numbers 	1			100			11 0	12 0	13 0	14 0	15 0			16	60		1999
Days	-56 to -1		1			29 +5	57 +5	85 +5	11 3 +5	14 1 +5			16 +!			199 ±5	
Weeks	-8 to -1	1				5	9	13	17	21			25			29	
Time (post- dose)	-	Predos e	0mi n	15mi n	45mi n	120mi n	-	-	-	-	-	-	0mi n	15mi n	45mi n	120mi n	-

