- Drug interrupted/permanently discontinued
- 6. Its outcome

Conditions that were already present at the time of informed consent should be recorded in medical history of the participant.

Adverse events (including lab abnormalities that constitute AEs) should be described using a diagnosis whenever possible, rather than individual underlying signs and symptoms.

Adverse event monitoring should be continued for at least 30 days following the last dose of study treatment.

Once an adverse event is detected, it must be followed until its resolution or until it is judged to be permanent (e.g. continuing at the end of the study), and assessment must be made at each visit (or more frequently, if necessary) of any changes in severity, the suspected relationship to the interventions required to treat it, and the outcome.

Information about adverse drug reactions for the investigational drug can be found in the Investigator's Brochure (IB).

Abnormal laboratory values or test results constitute adverse events only if they fulfill at least one of the following criteria:

- they induce clinical signs or symptoms
- they are considered clinically significant
- they require therapy

Clinically significant abnormal laboratory values or test results must be identified through a review of values outside of normal ranges/clinically notable ranges, significant changes from baseline or the previous visit, or values which are considered to be non-typical in participant with the underlying disease.

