### 12.5.2 Safety endpoints

For all safety analyses, the safety set will be used. All listings will be presented by treatment group and tables will be presented by treatment group and overall.

Safety summaries (tables, figures) include only data from the on-treatment period with the exception of baseline data which will also be summarized where appropriate (e.g. change from baseline summaries). In addition, a separate summary for death including on treatment and post treatment deaths will be provided. In particular, summary tables for adverse events (AEs) will summarize only on-treatment events, with a start date during the on-treatment period (treatment-emergent AEs).

The on-treatment period lasts from the date of first administration of study treatment to the EOS visit (about 30 days after the date of the last actual administration of any study treatment).

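### Table 8-1 dates the End of Study visit from Day 1 while the text dates it from the last dose; the on-treatment AE window ends at that visit and so inherits the conflict

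*Protocol*

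**What the plan says.** **Study-day anchor.** Protocol Section 3 has the end-of-treatment catheterization "performed at the end of the treatment period on Day 169 (Week 25"). The windows follow: "All visits from Week 5 to Week 25 have a plus 5 day visit window and Week 29 has a plus or minus 5 day". Table 8-1 gives the dates as Day 169 with +5 days and Day 199 with ±5 days. Its dosing footnote reads "Dosing is daily from Day 1 to Week 25 including all visit and non-visit days", and the table schedules a dose at the Week 25 visit.

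**Last-dose anchor.** The sentence in Section 3 just before the windows puts the follow-up visit about 30 days after treatment ends. Section 12.5.2 and SAP 2.1.1 and 2.7 describe EOS as about 30 days after the last actual administration. Exclusion criterion 9 has women use contraception "while taking study treatment and until End of Study visit (30 days post-last treatment").

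**What hangs on these dates.** Section 10.1.1: "Adverse event monitoring should be continued for at least 30 days following the last dose of study treatment". Section 10.1.3 collects SAEs to 30 days after the last administration. Section 12.5.2: "The on-treatment period lasts from the date of first administration of study treatment to the EOS visit", and AE tables take only events that start in that period. SAP 2.1.1 adds that the period ends at the last randomized dose when there is no EOS visit. Participants who enter the open-label extension skip EOS.

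**Early stoppers.** Section 8: "Participants who discontinue from study treatment are to return for the end of treatment visit as soon as possible, and attend the follow-up visits" set out in the Assessment Schedule. Section 9.1.1 says the same. The only EOS date in that schedule is Day 199 ± 5.

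**The concern.** A visit dated from Day 1 keeps a fixed distance from the last dose only if the last dose also has a fixed date. Here it does not: the Week 25 visit may slip by up to five days, and early stoppers may take their last dose at any time. Yet EOS closes the on-treatment period and, for women, is named as the end of the contraception requirement.

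Two opposite errors could follow.

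- **EOS too soon.** Section 10.1.1 has AEs sought by questioning at each visit, and no scheduled contact follows EOS. After an early EOS, the rest of the 30-day AE window has no visit at which events are solicited. Events reported then are still collected but fall outside the AE tables.
- **EOS too late.** If an early stopper is held to Day 199, AEs that start months after the last dose count as on-treatment. Section 9.1.1 requires stopping when disease progression calls for additional PAH therapy beyond what is allowed, so that period may include new PAH treatment.

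The groups are small. With 44 randomized 3:1 (33 and 11), one participant moved into or out of an AE row shifts it by 1/33 = 3.0 percentage points on LTP001 or 1/11 = 9.1 points on placebo.

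**Working it through.** **Inputs.** Week 25 visit: Day 169 to 174 (Table 8-1, +5). EOS: Day 194 to 204 (Table 8-1, 199 ± 5). Assumption: the last dose is taken on the day of the Week 25 visit, as the dosing footnote and the scheduled Week 25 dose imply.

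**1. The plan's own figure.** Nominal gap = 199 − 169 = 30 days. This reproduces the stated 30 days.

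**2. Range the windows permit in completers without extension entry.** Gap = EOS day − last-dose day.

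- Shortest: (199 − 5) − (169 + 5) = 194 − 174 = 20 days.
- Longest: (199 + 5) − 169 = 204 − 169 = 35 days.

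| Last dose (day) | Gap to EOS (days) | Permitted EOS days with a gap under 30 |
|---|---|---|
| 169 | 25–35 | 5 of 11 |
| 170 | 24–34 | 6 of 11 |
| 171 | 23–33 | 7 of 11 |
| 172 | 22–32 | 8 of 11 |
| 173 | 21–31 | 9 of 11 |
| 174 | 20–30 | 10 of 11 |

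Altogether 5 + 6 + 7 + 8 + 9 + 10 = 45 of 6 × 11 = 66 day pairs fall short of 30 days. If visits were spread evenly over both windows (an assumption with no source in the documents), the mean gap would be 199 − 171.5 = 27.5 days.

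**3. Part of the 30 days with no scheduled contact.** At most 30 − 20 = 10 days. For example, with a last dose on Day 174 and EOS on Day 194, an AE that starts on Day 199 is 25 days after the dose. It is inside the AE monitoring period of Section 10.1.1 but outside the on-treatment period of Section 12.5.2.

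**4. Early stoppers.** Under Table 8-1 read literally, gap = 199 − d, ± 5, for a last dose on Day d. Under the text, it is about 30 days.

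| Last dose (day) | Gap by Table 8-1 (days) | Gap by the text |
|---|---|---|
| 29 | 165–175 | about 30 |
| 57 | 137–147 | about 30 |
| 85 | 109–119 | about 30 |
| 113 | 81–91 | about 30 |
| 141 | 53–63 | about 30 |

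**5. Would a last-dose anchor alone suffice?** Last dose + 30 with ± 5 days gives 25 to 35 days for everyone. That removes the early-stopper problem, but still permits a visit five days short of 30.

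**The case against.** Most of the text already ties EOS to the end of treatment or the last dose, and only the table uses a study day. A reader might infer that the plan deliberately fixed EOS to the calendar in place of the last dose. The documents do not support that. They contain both anchors and leave them unreconciled.

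Other stronger readings also fail:

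- **Sites that keep to the schedule will under-deliver follow-up.** The AE and SAE duties run from the last dose whatever the EOS date, and Section 10.1.1 also accepts AEs volunteered between visits. A site that stops monitoring at day 20 breaches Section 10.1.1. What is missing is a scheduled contact and a place in the tables.
- **Every related window assumes 30 days.** Contraception for men ends 24 hours after the last dose, and the on-treatment period is only described as about 30 days.
- **About two thirds of completers (45/66 = 68%) will fall short.** That needs the unsourced even spread and counts a 29-day gap as a failure. The 20-day extreme is one pair of 66.
- **The comparison between arms is biased.** Both arms follow one schedule under blinding. No AE rate or difference between arms is available from which to show bias.

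The scope is limited too. Extension participants have no EOS. The planned dropout of around 10% of 44 is about four participants, and the Day 29 case is an illustration. Deaths are not lost, because post-treatment deaths are summarized.

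What the objection does not remove: about 30 days in one place cannot be squared with a permitted 20 where another section requires at least 30, and no rule tells a site which date applies to an early stopper.

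**Conclusion.** The point holds as an unreconciled contradiction with a consequence for the analysis. Followed as written, the windows permit 20 to 35 days from last dose to EOS in completers who do not enter the extension, so up to 10 of the required 30 days can lack a scheduled contact. Because the on-treatment period ends at the EOS visit, AEs that must be collected in those days are left out of the AE tables. For early stoppers the two anchors differ widely: for a last dose on Day 29, 165 to 175 days by the table against about 30 by the text.

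The 20-day minimum rests on the last dose being taken at the Week 25 visit. The early-stopper figures hold only if Table 8-1 is applied literally. The frequency of either problem cannot be derived from the documents. This should be corrected, but it does not touch the primary endpoint and does not by itself show a distorted safety comparison.

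**What to change.** 1. **Table 8-1 and Section 3.** Reconcile the table with the text so that EOS is counted from the actual last dose, for completers and early stoppers alike. Use a window that does not fall short of the protocol's own 30 days, for example last dose + 30 with 0 to +5 days. Have Sections 8 and 9.1.1 point to that rule.
2. **Protocol 12.5.2, SAP 2.1.1 and SAP 2.7.** End the on-treatment period at last dose + 30 days, not at the EOS visit date. The tables then cover the period that Sections 10.1.1 and 10.1.3 require, whenever the visit takes place.
3. **Extension participants.** They have no EOS, and SAP 2.1.1 falls back to the last randomized dose. That rule needs its own reconciliation with the start of extension dosing.
4. **Exclusion criterion 9.** It names two end dates for contraception, the EOS visit and 30 days after last treatment, and these can differ. The wording must be reconciled.

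Cost: amendment wording, a SAP edit and an EDC visit-window change. Some EOS visits move by up to about 10 days. No visit or procedure is added.

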# At the investigator's direction and based on benefit-risk considerations of the participant's clinical condition, qualifying participants may be offered the option to have certain clinical trial procedures performed at an off-site location, as defined in Table 8-1. A hybrid model is planned for this study incorporating both onsite and off-site visits. The off-site procedures will be

utilized in certain countries and sites as determined by protocol needs and based on national and local/site regulations. Participants have the option of participating in one or more off-site visits, based on their preference and the investigator's discretion.

One or more of the following elements may be implemented to support off-site visits where allowed by national and local regulations:

- Telemedicine
- Off-site Healthcare Professionals (OHP)
- Direct-to-patient shipment of study supplies
- Direct-to-patient shipment of study treatment (refer to Section 6)
- Electronic Source (eSource) Direct Data Capture (DDC)

Procedures for off-site visits utilizing the above listed elements are further detailed in the Science 37 Operational Manual and Nursing Manual of Operations and Procedures.

#### 3.1.1 Responsibility of investigators

Procedures that are performed off-site remain under the oversight of the investigator, who retains accountability for the conduct of all safety and efficacy assessments delegated to an OHP, and will ensure the rights, safety and wellbeing of participants. This includes the following (including, but not limited to):

- the identification, management and reporting of AEs and SAEs are performed in accordance with the protocol and applicable regulations including the review of PROs to identify any unreported AEs or SAEs.
- OHPs have appropriate qualifications, training, and experience to successfully conduct off-site procedures
- source data collected off-site are reviewed and evaluated in a timely manner
- the investigator or delegate is available to be contacted by the OHP if any issues or concerns are noted during an off-site visit
- where relevant, the investigator or delegate will be present via telemedicine for a portion of the off-site visit to support the physical examination

#### 3.1.2 **Responsibility of Off-site Healthcare Professionals**

OHPs must have the required qualifications, training, and experience to conduct off-site assessments. OHPs are responsible to conduct delegated assessments and collect relevant data at off-site visits in accordance with the clinical trial protocol, International Conference for Harmonization (ICH) Good Clinical Practice (GCP) guidelines, and national and local regulations and guidelines.

investigational site for review by the field monitor.

The OHPs will be provided by a third-party vendor sourced by Novartis. Where a site wishes to use OHPs that are not provided by Novartis this must be agreed with Novartis before use.

Any issues or safety concerns identified by the OHP will be promptly communicated to the investigator or delegate according to a pre-defined communication plan.

## 3.1.3 Telemedicine

The sponsor has qualified and contracted a third-party vendor to provide a telemedicine platform technology for this study. The selected platform is a validated system complying with relevant ICH E6 GCP guidelines. Trial participants can interact with site personnel using online communication tools built into the platform, enabling the following capabilities:

- Secure video conferencing which allows the patient, OHP and site personnel to be connected
- Reminders to be automatically sent to participants (e.g. visit or dosing reminders)
- eSource Direct Data Capture (DDC) (see Section 11.1.1)

